9.1.2 Baseline Visit (Day 1)

The following procedures will be conducted at this visit:

- 1. Record any changes in medical history since Screening.
- 2. Record changes in any previous BCC medications since the previous visit in eCRF. Check for prohibited concomitant therapies and confirm any therapy that requires a washout prior to Baseline as per Section 7.4.
- 3. Record changes in any concomitant medications since the previous visit in eCRF. Check for prior and concomitant therapies as per Section 7.4.

- 4. Verify that the subject continues to meet the applicable study eligibility criteria as outlined in Sections 6.1 and 6.2.
- 5. An abbreviated physical examination including measurements of weight.
- 6. The Investigator will perform the clinical evaluation to identify the treatment-targeted tumors which will be clinically classified as superficial, nodular, infiltrative, morphic, pigmented or micronodular/morpheaform to be circled in ink, photographed, measured, and recorded on a body diagram.
- 7. The Investigator or designee will assess the areas to be treated by observations and questioning the subjects as necessary for the signs and symptoms of irritation including pain/burning, pruritus, erythema, edema, and scabbing/crusting.
- 8. The Investigator will query the subject about the symptoms of any abnormalities in taste, frequency and severity of muscle cramps, recent changes in quality or quantity of hair in treated and untreated areas and any change in frequency of shaving of treated or untreated areas, any change in frequency of obtaining haircuts.
- 9. Randomize the subject to a treatment group and record the assigned kit number in the source document and in the eCRF.
- 10. The designated study drug staff will weigh each tube within the assigned kit and dispense them to the subject.
- 11. The Study Coordinator or designee will instruct the subject on the proper application procedure for the study drug. For the first application, the subject will apply the study drug at the investigational center under the direction of the Study Coordinator or designee. The study drug should be applied after all clinical assessments. The subjects will be asked to avoid exposure to direct sunlight on the initial application day and thereafter. The Study Coordinator or designee will instruct the subjects to apply the study drug once or twice daily at home and review patient instruction sheets and dosing card.
- 12. Record any AEs reported spontaneously by the subject.
- 13. If the subject is a woman of childbearing potential, the Study Coordinator or designee will provide the subject with three home pregnancy urine tests.
- 14. Schedule the next study visit at Week 2 (Day 15 ± 2 days).

9.1.3 Weeks 2, 6, 8, and 10

The following procedures will be conducted at this visit:

- 1. Record changes in any concomitant medications since the previous visit in the eCRF. Check for prior and concomitant therapies as per Section 7.4.
- 2. Record any new AEs reported spontaneously by the subject or changes in any ongoing AEs.
- 3. The treatment-targeted BCCs identified by the Investigator at the Baseline visit will be photographed and measured using the provided hand held device. *For the Week 6 visit*

- *only*, the treatment-targeted tumors will be, circled in ink, photographed, measured, and recorded on a body diagram.
- 4. The Investigator or designee will assess the treated areas by observations and questioning the subjects as necessary for the signs and symptoms of irritation including pain/burning, pruritus, erythema, edema, and scabbing/crusting.
- 5. The Investigator will question the subject about any concurrent illness or systemic sign or symptom including but not limited to fatigue, loss or change in taste, nausea, vomiting, diarrhea, muscle spasms or cramps, changes in quality or quantity of hair in treated areas and any change in frequency of shaving or haircuts.
- 6. Collect blood samples for routine laboratory analysis (CBC/Diff and serum chemistry) (*Weeks 6 only*).
- 7. If the subject is a woman of childbearing potential, they will take a home pregnancy urine test and disclose the results to the Investigator or designee (*Weeks 2, 8, and 10 only*).
- 8. The Study Coordinator or designee will weigh the previously dispensed study drug tube. The study coordinator or designee will weigh and dispense a new study drug tube from the subject assigned kit if necessary. (*Baseline and Week 6 only*)
- 9. Any missed doses or deviations should be reported.
- 10. The Study Coordinator or designee will remind the subject of the proper technique for application of the study drug. If needed, the subject can apply the study drug at the investigational center during the day under the direction of the Study Coordinator or designee to confirm proper technique.
- 11. Schedule the next study visit.

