Symptoms of Hedgehog Inhibitor Toxicity: At each visit subjects will be asked if they have experienced any symptoms that have been associated with systemic use of this class of drugs, in particular hair loss, taste loss, muscle cramps, bowel changes, fatigue.

Adverse Events: During the study, subjects will be assessed for the occurrence of new and ongoing AEs. Descriptions of AEs will include the dates of onset and resolution (if resolved), maximum severity, and seriousness, action taken regarding the study drug, corrective treatment, outcome, and the Investigator's assessment of causality. AEs present at any visit will be followed to resolution (return to normal or to the baseline state) or until clinically stable as determined by the Investigator.

Safety Laboratory Tests: Routine safety laboratory tests (complete blood count/differential urinalysis and serum chemistry) will be performed at Screening, Week 6, and Week 12. Any out-of-range laboratory result that is considered clinically significant by the Investigator will be recorded as an AE and should be confirmed by repeat testing at the discretion of the Investigator. Clinically significant laboratory abnormalities at any visit will be followed to resolution (return to normal or to the baseline state) or until clinically stable as determined by the Investigator.

Physical Examinations: An abbreviated physical examination including measurements of height, weight, and vital signs (blood pressure, heart rate, respiration rate, and oral temperature) will be performed at Baseline and Week 12.

Pregnancy Tests: All female subjects will have a pregnancy test performed at the Screening visit. Females of childbearing potential will take a home pregnancy urine test at Weeks 2, 8, and 10 and will have a serum pregnancy test at Weeks 6 and 12.

Efficacy Measurements:

Primary:

Biomarker: At screening the treatment-targeted BCC will be biopsied to confirm the clinical diagnosis of nodular BCC. In addition, at or within 14 days of the Week 12 visit the

treatment site will be excised. Both of these tissue samples will be tested for GLI1 mRNA levels.

Secondary:

The clinical efficacy of patidegib as defined by the percent decrease from Baseline of the longest diameter of treatment-targeted BCC after 12 weeks of treatment.

Exploratory:

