6.6 Stopping Criteria

Sponsor will monitor frequency of systemic signs and symptoms associated with this class of drug as well as any lab abnormalities. If clinically significant signs or symptoms of hedgehog inhibitors are detected, in particular hair loss, taste loss, muscle cramps, bowel changes, fatigue, as well as abnormal liver function tests, dosing will be stopped.

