9.1.4 Week 12 (Day 85 ± 3 Days) / Early Termination

The following procedures will be conducted at this visit:

- 1. Record changes in any concomitant medications since the previous visit in the eCRF. Check for prior and concomitant therapies as per Section 7.4.
- 2. Record any new AEs reported spontaneously by the subject or changes in any ongoing AEs. Record subject weight.
- 3. Perform a brief physical exam including vital signs and weight.
- 4. Collect blood samples for routine laboratory analysis (CBC/Diff and serum chemistry).
- 5. The Investigator or designee will assess the treated areas by observations and questioning the subjects as necessary for the signs and symptoms of irritation including pain/burning, pruritus, erythema, edema, and scabbing/crusting.
- 6. The treatment site(s) will be excised.
- 7. The Investigator will question the subject about any concurrent illness or systemic sign or symptom including but not limited to fatigue, loss or change in taste, nausea,

PellePharm, Inc.

Dose Escalating in Sporadic Basal Cell Carcinomas

vomiting, diarrhea, muscle spasms or cramps, changes in quality or quantity of hair in treated areas and any change in frequency of shaving.

- 8. The Study Coordinator or designee will collect and weigh the previously dispensed study drug tube.
- 9. Any missed doses or deviations should be reported.
- 10. Exit the subject from the study and complete the end of study eCRFs.

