Table	14.2.4.4: Analysis of the Ex	xploratory Efficacy Endpo	int: Area of Baseline Trea	nted Tumors based on Pho	otographic Review (Per Pr	rotocol Population)
Analysis Pla	n for PellePharm, Inc.			Page 40		
umber: 926-	202			Page 40 28Sep2017		

Table 14.3.1.2.1: Summary of Dermal Safety and Tolerability (Safety Population)
(Page 1 of x)

Pain / Burning	Patidegib Gel 2% QD (N=xx)	Patidegib Gel 2% BID (N=xx)	Patidegib Gel 4% QD (N=xx)	Patidegib Gel 4% BID (N=xx)	Vehicle Gel (N=xx)
Baseline					
Number of tumors	XX	XX	XX	XX	XX
None	xx (xx.x%)	xx (xx.x%)	xx (xx.x%)	xx (xx.x%)	xx (xx.x%)
Mild	xx (xx.x%)	xx (xx.x%)	xx (xx.x%)	xx (xx.x%)	xx (xx.x%)
Moderate	xx (xx.x%)	xx (xx.x%)	xx (xx.x%)	xx (xx.x%)	xx (xx.x%)
Severe	xx (xx.x%)	xx (xx.x%)	xx (xx.x%)	xx (xx.x%)	xx (xx.x%)
Week 2					
Number of tumors	XX	XX	XX	XX	XX
None	xx (xx.x%)	xx (xx.x%)	xx (xx.x%)	xx (xx.x%)	xx (xx.x%)
Mild	xx (xx.x%)	xx (xx.x%)	xx (xx.x%)	xx (xx.x%)	xx (xx.x%)
Moderate	xx (xx.x%)	xx (xx.x%)	xx (xx.x%)	xx (xx.x%)	xx (xx.x%)
Severe	xx (xx.x%)	xx (xx.x%)	xx (xx.x%)	xx (xx.x%)	xx (xx.x%)

Continue for Weeks 6, 8, 10, 12

Repeat for Pruritus, Erythema, Edema, Scabbing / Crusting

Note: Local safety and tolerability is reported by the subject as the greatest intensity since the last visit or within 24 hours at Baseline.

Table 14.3.1.2.2: Summary of Systemic Symptoms (Safety Population) (Page 1 of x)

Fatigue Baseline	Patidegib Gel 2% QD (N=xx)	Patidegib Gel 2% BID (N=xx)	Patidegib Gel 4% QD (N=xx)	Patidegib Gel 4% BID (N=xx)	Vehicle Gel (N=xx)
n	xx	XX	XX	XX	XX
Yes	xx (xx.x%)	xx (xx.x%)	xx (xx.x%)	xx (xx.x%)	xx (xx.x%)
No	xx (xx.x%)	xx (xx.x%)	xx (xx.x%)	xx (xx.x%)	xx (xx.x%)
Week 2					
n	XX	XX	XX	XX	XX
Yes	xx (xx.x%)	xx (xx.x%)	xx (xx.x%)	xx (xx.x%)	xx (xx.x%)
No	xx (xx.x%)	xx (xx.x%)	xx (xx.x%)	xx (xx.x%)	xx (xx.x%)
Week 6					
n	XX	XX	XX	XX	XX
Yes	xx (xx.x%)	xx (xx.x%)	xx (xx.x%)	xx (xx.x%)	xx (xx.x%)
No	xx (xx.x%)	xx (xx.x%)	xx (xx.x%)	xx (xx.x%)	xx (xx.x%)

Continue for Weeks 8, 10, 12

Repeat for Loss or Change in Taste, Nausea, Vomiting, Diarrhea, Muscle Spasms or Cramps, Changes of Quality or Quantity of Hair in Treated Areas, Change in Frequency of Shaving, Other Systemic Sign or Symptoms, Other

Table 14.3.2.1.1: Summary of Treatment-Emergent Adverse Event Characteristics (Safety Population)
(Page 1 of 2)

	Patidegib Gel 2% QD (N=xx)	Patidegib Gel 2% BID (N=xx)	Patidegib Gel 4% QD (N=xx)	Patidegib Gel 4% BID (N=xx)	Vehicle Gel (N=xx)

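### Two of the five class symptoms named in the stopping criteria, hair loss and bowel changes, have only narrowed items in the visit questions after Baseline and in the SAP symptom table

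*Protocol*

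**What the plan says.** Protocol 6.6 (Stopping Criteria) has the sponsor monitor systemic signs and symptoms of the class: "in particular hair loss, taste loss, muscle cramps, bowel changes, fatigue, as well as abnormal liver function tests, dosing will be stopped". The Synopsis, under hedgehog inhibitor toxicity, has subjects asked at each visit about symptoms seen with systemic use, "in particular hair loss, taste loss, muscle cramps, bowel changes, fatigue". Neither place sets an area limit for hair or restricts bowel change to one kind.

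The visit lists are worded differently from these and from each other:

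- **Baseline, 9.1.2 step 8:** taste, muscle cramps, "recent changes in quality or quantity of hair in treated and untreated areas", then shaving frequency (both kinds of area) and haircut frequency.
- **Weeks 2, 6, 8 and 10, 9.1.3 step 5:** "any concurrent illness or systemic sign or symptom including but not limited to fatigue, loss or change in taste, nausea, vomiting, diarrhea", then cramps and "changes in quality or quantity of hair in treated areas and any change in frequency of shaving or haircuts".
- **Week 12 / Early Termination, 9.1.4 step 7:** the same lead-in and items, ending with "changes in quality or quantity of hair in treated areas and any change in frequency of shaving". The haircut item is gone.

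Table 1 schedules Systemic Symptoms at Baseline and at all five later treatment visits. SAP 6.8.4.2 summarizes them by treatment group and visit. The shell for Table 14.3.1.2.2 has rows for fatigue, taste, nausea, vomiting, diarrhea, cramps, "Changes of Quality or Quantity of Hair in Treated Areas", shaving frequency and two catch-all items. Listing 16.2.7.1.2 has the same named items and one catch-all, printed with its specification when marked Yes.

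Protocol 9.3.5.2 separately has subjects questioned about an open list that includes alopecia, with no area limit, and diarrhea. Any incidence goes to the adverse event eCRF.

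**The concern.** Hair loss from systemic exposure would not be confined to the skin under the gel. A hair question limited to treated areas asks where a local effect would show. It does not ask where a systemic one would.

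Safety and tolerability is the first primary objective. Inclusion Criterion 3 calls systemic exposure after topical use unknown, and neither Table 1 nor the laboratory list in 15.2 includes a drug-level sample. Symptom questioning therefore carries much of the evidence on systemic effect, and Table 14.3.1.2.2 is where that evidence is set out by regimen and visit.

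Two more gaps affect the same table. Haircut frequency, the item that bears most directly on scalp hair, disappears at Week 12, the end of treatment, and has no SAP row. Baseline step 8 names neither fatigue nor any bowel item, yet the SAP shells expect Baseline entries for both.

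**Working it through.** The plan states no figure on this point. The check is an item-by-item comparison for the five symptoms in Protocol 6.6.

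| Symptom (6.6, Synopsis) | Baseline, 9.1.2 step 8 | Weeks 2–10, 9.1.3 step 5 | Week 12, 9.1.4 step 7 | SAP Table 14.3.1.2.2 |
|---|---|---|---|---|
| Taste | yes | yes | yes | yes |
| Cramps | yes | yes | yes | yes |
| Fatigue | not named | yes | yes | yes, with a Baseline row |
| Hair | treated and untreated; shaving; haircuts | treated; shaving; haircuts | treated; shaving | treated; shaving |
| Bowel | not named | diarrhea | diarrhea | diarrhea, with a Baseline row |

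**Counts**

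- Fully itemized after Baseline and in the SAP: taste, cramps, fatigue = 3 of 5.
- Narrowed: hair and bowel = 5 − 3 = 2 of 5. Hair is narrower than both 6.6 and the Baseline question. Bowel is narrower than 6.6 and the Synopsis.
- Not named in Baseline step 8: fatigue and bowel = 2 of 5.
- Haircut frequency: asked at Baseline and Weeks 2, 6, 8 and 10 = 5 of 6 visits, with no SAP row.

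**Routes left for an unlisted event.** Scalp hair loss first noticed at Week 12 matches no named item unless the subject also shaves less often. Otherwise it depends on the open lead-in and then falls in a catch-all row, which the table shell does not break down by symptom. A bowel change other than diarrhea has only the catch-all.

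**Illustration of sensitivity to capture.** Each cohort has n = 6 active subjects (Protocol 5.1). Let p be the true proportion with the symptom and s the share of true cases that the by-visit item records. Both are assumptions; the documents give neither. With independent subjects, P(at least one recorded case) = 1 − (1 − p·s)^n. For p = 0.20 and s = 1: 1 − 0.80^6 = 1 − 0.262 = 0.738. For s = 0.5: 1 − 0.90^6 = 1 − 0.531 = 0.469.

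| p | s = 1 | s = 0.75 | s = 0.5 | s = 0.25 |
|---|---|---|---|---|
| 10% | 0.469 | 0.374 | 0.265 | 0.141 |
| 20% | 0.738 | 0.623 | 0.469 | 0.265 |
| 30% | 0.882 | 0.783 | 0.623 | 0.374 |

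With six subjects on each active regimen, incomplete capture can decide whether that regimen's column shows a case at all. The table says nothing about what s would be in practice.

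**The case against.** The strongest reply is that this is uneven wording and that no assessment is absent:

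- The visit question is open-ended, and the Synopsis separately requires the broad question at each visit.
- Shaving has no area limit after Baseline, nor do haircuts at Weeks 2–10.
- The SAP table has two catch-all items, and the listing prints what was specified.
- Protocol 9.3.5.2 asks about alopecia anywhere and sends it to the adverse event eCRF. Scalp alopecia would then appear by regimen and preferred term in Table 14.3.2.1.2.
- Table 1 schedules Systemic Symptoms at Baseline, and Listing 16.2.7.1.2 shows Baseline entries for fatigue and diarrhea.
- Section 6.6 does not tie the sponsor's monitoring to this table.

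Most of this stands and limits the point, but it does not remove it. Shaving and haircuts are proxies. A catch-all row cannot show one symptom by regimen. The treatment-emergent event tables are not by visit and give no comparison with Baseline. Section 9.3.5.2 also names only diarrhea. Step 2 of 9.1.3 and 9.1.4 refers to new events that the subject reports spontaneously, so the symptom and event tables could disagree. Table 1 and the shells show that Baseline values are intended, which makes the shorter list in step 8 an inconsistency to be settled.

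**Conclusion.** The point holds for two of the five named symptoms. After Baseline, hair quality and quantity are asked about and tabulated for treated areas only, and diarrhea stands in for bowel changes. Missing items for haircuts (Week 12 and SAP) and for fatigue and bowel (Baseline step 8) add to the inconsistency. For hair and bowel, the likely direction is too few events in the by-visit table. A missing Baseline fatigue value could mislead either way.

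A reader might infer more than the documents support:

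- **That the by-visit data would miss the class toxicities in general, or make every regimen look systemically clean.** Three of the five are itemized after Baseline. For the other two, the proxies, the catch-all rows and the adverse event route would all have to fail.
- **That the stopping criteria would not be triggered.** Section 6.6 does not depend on this table.
- **That the small area of treated skin measures the loss.** Area says nothing about how many events go unrecorded, and no capture rate can be derived.

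The conclusion assumes that sites and the eCRF follow 9.1.2–9.1.4 as written; the eCRF is not among the documents. It takes no position on the stopping criteria themselves.

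**What to change.** Reconcile the Protocol Synopsis (hedgehog inhibitor toxicity), 6.6, 9.1.2 step 8, 9.1.3 step 5, 9.1.4 step 7 and 9.3.5.2 with SAP Table 14.3.1.2.2 and Listing 16.2.7.1.2, so that all use one symptom list:

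1. Use the same list at Baseline and at Weeks 2, 6, 8, 10 and 12, covering every symptom already named in 6.6 and the Synopsis. This adds fatigue and bowel to Baseline step 8.
2. Keep the Baseline scope for hair at all visits, with treated and untreated areas recorded as separate items.
3. Keep both shaving and haircut frequency at all visits, including Week 12.
4. Use bowel changes, the term in 6.6, as the bowel item.
5. Give each item its own row in the SAP table and listing, with a Baseline value.

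The cost is a few eCRF fields, a few table and listing rows, and edits to the visit lists. No visit, test or staff is added. Only data capture and display change.

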9.1.4 Week 12 (Day 85 ± 3 Days) / Early Termination

The following procedures will be conducted at this visit:

- 1. Record changes in any concomitant medications since the previous visit in the eCRF. Check for prior and concomitant therapies as per Section 7.4.
- 2. Record any new AEs reported spontaneously by the subject or changes in any ongoing AEs. Record subject weight.
- 3. Perform a brief physical exam including vital signs and weight.
- 4. Collect blood samples for routine laboratory analysis (CBC/Diff and serum chemistry).
- 5. The Investigator or designee will assess the treated areas by observations and questioning the subjects as necessary for the signs and symptoms of irritation including pain/burning, pruritus, erythema, edema, and scabbing/crusting.
- 6. The treatment site(s) will be excised.
- 7. The Investigator will question the subject about any concurrent illness or systemic sign or symptom including but not limited to fatigue, loss or change in taste, nausea,

PellePharm, Inc.

Dose Escalating in Sporadic Basal Cell Carcinomas

vomiting, diarrhea, muscle spasms or cramps, changes in quality or quantity of hair in treated areas and any change in frequency of shaving.

- 8. The Study Coordinator or designee will collect and weigh the previously dispensed study drug tube.
- 9. Any missed doses or deviations should be reported.
- 10. Exit the subject from the study and complete the end of study eCRFs.

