Measure and Map BCCs	X	X	X	X	X	X	X	
Determine Clinical Tumor Type	X							
2mm Punch or Shave Biopsy	X							
End of Treatment Excision							Xh	
BCC Imaging ^I	X	X	X	X	X	X	X	

PellePharm, Inc.

Dose Escalating in Sporadic Basal Cell Carcinomas

Systemic Symptoms		X	X	X	X	X	X	
Patidegib /Vehicle Applications ^J		X	X	X	X	X		
Study drug review/Instructions Dispensation ^J		X	Х	х	х	Х		
Concomitant Medications	X	X	X	X	X	X	X	
Adverse Events	X	X	X	X	X	Х	X	
Review Test Article Compliance/Accountability		X	х	Х	Х	Х	Х	
Clinical Evaluation of Surgical Site(s)								X

BCC= basal cell carcinoma; ET = early termination; ISGTA = investigator static global tumor assessment;

- a for subjects who discontinue early during the treatment period, all procedures outlined for the ET visit should be completed at the time of discontinuation.
- b Must be signed prior to any study procedures.
- ^c Medical history will be updated at Baseline visit.
- d Height will be measured at Baseline only.
- ^e Blood samples for laboratory tests will be collected at Screening. Clinically significant laboratory findings at Week 6 or Week 12 will be repeated at the discretion of the Investigator, and the subject will be followed until resolution (return to normal or to the baseline state) or until clinically stable as determined by the Investigator.
- f Week 6 and 12 serums to be done only for women of child bearing potential
- 8 Only to be done for women of child bearing potential
- h Must be within 48 hours of the Week 12 visit.
- ¹ Imaging requirements are provided in the imaging manual.
- Jubjects will be trained on how to administer the study drug at the Baseline visit and retrained at subsequent visits, if necessary. The study drug may be applied at the study visit. Subjects will record any missed doses and provide to the study site for review

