9.1.5 Week 14 (Day 99 \pm 7 Days) / Post Operation Follow-up

The following procedures will be conducted at this visit:

1. The Principal Investigator will do a clinical evaluation of the surgical site(s) to confirm adequate healing.

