9.3.5.2 Documenting Adverse Events

It is the responsibility of the Investigator to document all AEs that occur during the course of the study. The AEs should be documented as a single medical diagnosis. When this is not possible, the AE should be documented in terms of signs and/or symptoms observed by the Investigator or reported by the subject at each study visit.

All AEs occurring after the subject signs the informed consent through the last study visit must be reported, regardless of whether or not the AEs are considered drug-related. All AEs, whether in response to a query, observed by the study site personnel, or reported spontaneously by the subject, will be recorded.

At each visit during the study, the subject will be assessed for the occurrence of new and ongoing AEs. Dermal safety and tolerability that result in the subject's requiring a concomitant therapy or discontinuation from the study will be reported as an AE. The following data will be collected on all AEs and recorded on the appropriate CRF:

- Event name (diagnosis preferred, if unknown, record the signs/symptoms)
- Onset date and end date
- Maximum intensity (severity)
- Seriousness
- Action taken regarding study drug
- Corrective treatment, if given
- Outcome

In addition, the Investigator's assessment of causality will be recorded.

Vital sign abnormalities are to be recorded as AEs only if they are clinically significant (for example: are symptomatic, requiring corrective treatment, leading to discontinuation or fulfilling a seriousness criterion).

Subjects will be questioned about any concurrent illness or systemic sign or symptom including but not limited to fatigue, loss or change in taste, nausea, vomiting, alopecia, diarrhea, and muscle spasms. Any incidence of these systemic signs or symptoms will be reported on the AE eCRF.

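### The visit schedule stops adverse event collection and exits subjects at Week 12, although the protocol's own rules carry collection through the Week 14 post-operative visit

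*Protocol*

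**What the plan says.** Protocol Section 9.1.4 covers Week 12 and early termination in one list of ten steps. Step 2 reads "Record any new AEs reported spontaneously by the subject or changes in any ongoing AEs", step 6 reads "The treatment site(s) will be excised", and step 10 reads "Exit the subject from the study and complete the end of study eCRFs".

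Section 9.1.5 then sets a Week 14 post-operative visit at Day 99 ± 7 with a single procedure: "The Principal Investigator will do a clinical evaluation of the surgical site(s) to confirm adequate healing". Table 1 agrees with it: the surgical-site evaluation is the only row marked in the Week 14 column.

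Section 9.3.5.2 sets the rules for AEs. On the period it says "All AEs occurring after the subject signs the informed consent through the last study visit must be reported". On frequency it says "At each visit during the study, the subject will be assessed for the occurrence of new and ongoing AEs". The Methodology part of the synopsis also has AE information obtained at every visit.

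Section 9 lists Week 14 among the in-person study visits. Section 6.3 provides for subjects who discontinue during post-treatment follow-up. SAP Section 6.1.3 gives Week 14 its own analysis window, Day 92 to 106.

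**The concern.** A site that works from Table 1 and Sections 9.1.4 and 9.1.5 would complete the end-of-study forms at Week 12 and have no prompt to ask about AEs or update medications afterwards. A site that works from Section 9.3.5.2 would ask at Week 14. Both would be following the protocol.

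The gap falls where new events are plausible. The protocol requires excision of the whole original tumor area, on one or two sites per subject, and study drug may be applied up to the Week 12 visit (Section 8.4). Safety and tolerability is the first primary objective. With only six active subjects planned per cohort, a few events recorded at one site location and not at another could change how an arm looks.

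**Working it through.** The plan states no figure to reproduce. The check compares passages and does calendar arithmetic on the visit windows.

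**1. Is Week 14 scheduled for AE collection?** Table 1 has 8 visit columns: Screening, Baseline, Weeks 2, 6, 8, 10, 12 and 14. The AE row has 7 marks and the concomitant medication row has 7 marks. In both, the blank is Week 14. Section 9.1.5 adds neither.

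**2. Could Week 12 be the last study visit?** That reading would remove the conflict, but three passages speak against it:
- Section 9 names Week 14 as a study visit.
- Section 6.3 lets subjects discontinue during post-treatment follow-up, which cannot happen if all have exited at Week 12.
- SAP Section 6.1.3 includes Week 14 in its windows for efficacy and safety assessments.

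**3. Length of the interval without scheduled collection.**
- Week 12 window: 85 − 3 = Day 82 to 85 + 3 = Day 88.
- Week 14 window: 99 − 7 = Day 92 to 99 + 7 = Day 106.
- Nominal: 99 − 85 = 14 days.
- Shortest: 92 − 88 = 4 days. Longest: 106 − 82 = 24 days.

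These are days between visits. They equal days since surgery only if excision takes place on the Week 12 visit day.

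**4. How many subjects and sites?** About 36 subjects are planned, each with one or two target tumors. If all 36 are excised, the number of sites lies between 36 × 1 = 36 and 36 × 2 = 72. Both 36 subjects and 72 sites are ceilings.

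**5. Where does excision fall relative to AE collection?** The protocol gives three timings:
- Sections 5.1 and 9.1.4: at the Week 12 visit. The AE step is listed before the excision step, and no AE step comes after it. The list does not say that its order is binding.
- Table 1, footnote h: within 48 hours of Week 12, so as late as 88 + 2 = Day 90.
- Synopsis, efficacy measurements: up to 14 days from Week 12, so as late as 88 + 14 = Day 102.

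Under the second and third timings, surgery can come after the subject has been exited. Under the third it can also come after the earliest permitted Week 14 visit, by 102 − 92 = 10 days. In that case a healing check on Day 92 would precede the surgery it is meant to follow.

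**6. Does the analysis plan set an end to AE collection?** No. Protocol Section 10.8.2 and SAP Section 6.8.2 define treatment-emergent AEs by onset on or after first application and give no closing date.

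**The case against.** The best counter-argument is that the general rules already cover Week 14. Section 9.3.5.2 makes reporting mandatory through the last study visit, whether an event is elicited, observed or volunteered. Section 9.3.5.6 sends anything found on examination to the AE form and has AEs followed until they resolve or stabilize. On this view only a prompt is missing. This largely stands. A reader might infer that post-excision safety data are lost; the documents do not support that. They support a risk of missed or uneven recording.

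A reader might also infer that wound complications go unobserved. They do not: the Principal Investigator examines the site at Week 14, and SAP Listing 16.2.8.5 reports whether healing is adequate, with text if not. That listing has no fields for severity, seriousness, causality or action taken, and it does not reach non-wound events.

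A third inference is that the primary safety objective is compromised. That objective concerns tolerability of 12 weeks of gel, and surgery follows in every arm, so surgical events bear on it only indirectly. Late events after the last application bear on it more directly, and they share the same gap.

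Finally, one might think the SAP would exclude events recorded at Week 14. Because the treatment-emergent definition is open-ended, it would not.

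**Conclusion.** The protocol contradicts itself on when a subject leaves the study and when AE collection ends. The consequence is that new post-operative and late post-treatment AEs may be missed or recorded inconsistently over a nominal 14 days, 4 to 24 days between visits, in up to 36 subjects and at most 72 excision sites. The upper counts assume full enrolment, excision in everyone and two tumors each.

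The conclusion rests on reading Week 14 as a study visit, which Section 9 says outright. It does not depend on which excision timing applies, though the unresolved timing makes the gap worse. This is a moderate defect that should be corrected: the general AE rules and the healing check soften it, but neither schedules detection of new events.

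**What to change.** Reconcile Sections 9.1.4, 9.1.5 and 9.3.5.2 with Table 1:
- Move the exit step and the end-of-study eCRFs to Week 14 for subjects who are excised.
- Keep an exit step at the early termination visit for subjects who will have no Week 14 visit. Step 10 now serves both groups, so moving it without this would leave them with no exit step.
- Add AE and concomitant medication collection to the existing Week 14 visit, in Section 9.1.5 and in Table 1.
- Reconcile the three excision-timing statements (at the Week 12 visit, within 48 hours, within 14 days) so that the Week 14 visit always follows excision. Which timing applies is for the sponsor and investigator to settle.

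A sentence in the SAP that treatment-emergent summaries run through Week 14 would be useful but is optional, because the definition has no end date.

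The cost is two marks in Table 1, matching lines in Section 9.1.5, a relocated exit step with a short early-termination rule, and one agreed excision timing. No visit or procedure is added.
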